Randomisation will be undertaken by the King's College London Clinical Trials Unit (CTU) after informed consent/assent is given and baseline assessment is complete. This will use block randomisation with randomly varying block sizes of 4 or 6 with equal allocation ratio in order to ensure the research team are blind to the randomization outcome. We will use small block sizes to ensure full caseloads for the clinical teams. We will stratify by site and randomisation will be conducted individually rather than in batches. When randomisation is complete, the researcher informs the referring practitioner and the FFT-G supervisor/supervisor-in-training of the outcome. Families are then informed of the outcome of randomisation by the referring practitioner and then are informed in more detail about the relevant intervention. The researcher is blind to treatment allocation during the baseline assessment but cannot be blind to allocation during post-treatment assessment. Families are not blind to treatment allocation.

Participants

Participants will be YP between 10-17 at risk of CLDN involvement or CCE being seen by child social care or related agencies in three London local authorities and their primary caregiver (PCG).

Inclusion criteria – YP and families

We use broader criteria identified by the Child Safeguarding Practice Review Panel (2020) for CCE/CLDN involvement, with a view to further screening undertaken subsequently in consultation:

Child/ young person aged between 10–17 years

AND

ONE OR MORE OF:

- Known to services due to concerns in the last 12 months around:
 - Child sexual exploitation (CSE)
 - Child criminal exploitation (CCE)
 - Missing (from home or care) episodes
 - Potential or actual gang or CLDN affiliation as identified by police or other statutory service
 - Repeated school exclusion or absence
 - Involvement as a perpetrator or victim of youth violence or criminality

OR

TWO OR MORE OF THE FOLLOWING (OVER THE LAST 12 MONTHS):

- Family conflict or inadequate supervision
- Associating with antisocial peers
- Concerns about alcohol or drug use

AND EITHER

- Index child/young person is living at home 50% or more each week.

OR

- Index child/young person is currently in an out of home placement, but with a clear return home plan (discussed on a case by case basis).

AND

- Caregiver(s) and index child/young person are willing to engage in family therapy.

Exclusion criteria – YP and families:

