Towards the end of the call, the FPM referral and data officer is invited to join the call and i) explain the study to the practitioner in more detail, ii) provide their contact details, iii) ask the practitioner to provide an information sheet to and request consent from the family for their contact details to be shared with the research team and then iv) set up a first call with the family.

[figure not shown]
Consent and assessment

The Greenwich Research Assistant (RA) meets the YP and PCG either via a Microsoft Teams video call, on the telephone or in a face-to-face meeting (in the family home or neutral venue), and explains the study to the family (PCG and YP) and obtains consent⁸. Typically, this will take place over a number of calls/meetings. If consent is given the RA will then conduct the baseline research assessment with the YP and their PCG separately. This will be in the form of an interview for the majority of cases. If the participants wish to complete the measures online on their own, then the link to a Redcap survey is provided (please also see description of primary outcome below). Translated study materials and/or interpreters will be used when required to enable informed consent and to complete the research tools.

The intervention is typically delivered in the family home or in a neutral venue if that is preferred by the family.

⁸ When it is only possible to obtain verbal consent, participants will subsequently be contacted to attempt to obtain written consent.

Figure 2: CONSORT diagram

n.b. example CONSORT diagram with anticipated numbers.

Sample size calculations

Sample size calculations are not determined on the basis of a priori MDES but rather data from the pilot RCT. [note difference from primary outcomes and direct to outcomes section for full explanation].

Sample size estimates for a full efficacy RCT were calculated using clincalc.com and checked against G*Power calculations. Estimates used 80% power and $p = 0.05$ with an enrolment ratio of 1. Power calculations used one-sided tests because there is no recorded case of FFT having iatrogenic effects.

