Thus, YP will complete either a hardcopy or online version of these outcome measures that will not be linked to any identifying information on our systems and will therefore be completely anonymous. Researchers will provide support to YP in answering questions as requested without having full access to participant response. We will also collect some secondary outcomes using this method, including data on CCE. We will include a paragraph at the end of the measure saying that they can talk to the researcher or to their caseworker if they are being hurt, criminally exploited or feel at risk of being so. We will then make a referral but the data for the primary outcome measure will remain anonymous.

Secondary outcomes

YP mental health and adjustment (25 items) and impact items (5 items) (Both parent and YP report: Strengths and Difficulties Questionnaire; Goodman, 2005). This measure is associated with FFT-identified risk factors situated within the individual domain (i.e., index young person) and with proximal outcomes, e.g., reduction in internalizing and externalizing behaviours. We will total SDQ score and each five item subscore (conduct problems, ADHD, emotional problems, peer problems, prosocial behaviour) and collect the impact score. Taken together, these will measure YP mental health and adjustment. This will be done separately for parent report SDQ and YP report SDQ.

The impact supplement provides additional information on any difficulties a child or young person displays in emotions, concentration, behaviour or social relationships, including information on chronicity, distress, social impairment and burden to others.

Child Criminal Exploitation (YP report: ISRD4; Marshall et al., 2022: 2 additional questions and up to 3 follow-on questions). For each of the ISRD4 offending scale items we will add follow-on questions to each of the 14 items:

Have other people in your life tried to involve you in this behaviour? [CCE lifetime prevalence]
Who tried to involve you? [checklist]

Your friend(s)

A sibling

Other young people you know

An adult in your family

Another adult

Other [Please explain their relationship to you]

If yes [to each of the above], how many times in the last 6 months? [CCE 6 month incidence]

We will also add three additional questions which will be used to prompt for CCE/CSE information (as above) and will not contribute to the primary outcome: ISRD offending scale:

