The size of the FFT teams was decided upon the capacity needed to work with 144 families over the randomisation period. To generate this capacity we considered 3 teams, each with 2 therapists and 1 supervisor. This will give a capacity of 14 cases over 5 months for each team. Each team will be able to recruit 3-4 new families over 15 months (cycles of 5/6 months to allow completion of cases) for the RCT. There will of course be some attrition which will create some flexibility, but we need to aim for full capacity on completion.

The 3 teams will each be supported by a part time business officer. We will allocate one day a week of input from the Data Analyst and ongoing oversight from the Programme Manager. Leadership will be provided by the full time Programme Manager and part time (three days a week) Programme Director for general oversight. The Programme Manager and Data Analyst will be the main contact points to liaise with the Greenwich research team and to ensure the collection of all necessary data from the teams. To this central FPM administration team, we also propose adding a Data and Referral Officer. The postholder will set up the initial meeting between the family and research team (and all other associated administrative tasks), but will remain blind to research data and will only have access to the FPM/University of Greenwich case tracker spreadsheet to ensure oversight of recruitment and throughput issues. They will have no role in the administration of research questionnaires or consent forms although may collect them in a sealed envelope.

Evaluation team:

The senior evaluation team will consist of some the same team that led the YEF funded pilot feasibility trial of FFT-G, namely, [name] (PI; University of Greenwich), and

Professor (Co-I) [name] (Co-I; Royal Holloway, University of London). In addition, [name] (Co-I; University of Greenwich) will also be a Co-I. The team will also consist of a research team consisting of one Research Fellow and up to three research assistants.

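### Each allocation reaches the clinical side through the researcher role that later collects outcomes, an avoidable unblinding route for researcher-collected secondary outcomes and mediators

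*Protocol*

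**What the plan says.** The Randomisation section of the protocol sets out the chain. "Randomisation will be undertaken by the King's College London Clinical Trials Unit (CTU) after informed consent/assent is given and baseline assessment is complete". Then: "When randomisation is complete, the researcher informs the referring practitioner and the FFT-G supervisor/supervisor-in-training of the outcome". The practitioner tells the family. The section continues: "The researcher is blind to treatment allocation during the baseline assessment but cannot be blind to allocation during post-treatment assessment", and "Families are not blind to treatment allocation". Earlier in the same section, randomly varying blocks of 4 or 6 are chosen "in order to ensure the research team are blind to the randomization outcome". The SAP, Design overview, repeats that aim and says nothing further about who is blind at outcome assessment.

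Under Outcome data collection points, a University of Greenwich researcher collects all measures at baseline, 6 and 12 months unless specified otherwise. Under Stakeholders and interests, the field team is one Research Fellow and up to three research assistants, and the assistants do most of the recruitment and assessment.

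On mode, Consent and assessment says of the baseline assessment: "This will be in the form of an interview for the majority of cases". Participants who prefer it may complete the measures online by themselves.

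The primary outcome and some secondary outcomes, including child criminal exploitation, are handled differently (Method of collection for offending and CCE data). The young person completes them on paper or online under a separate ID. A different Greenwich team stores them, and the study team has no access until the end of the study. On help with these measures: "Researchers will provide support to YP in answering questions as requested without having full access to participant response".

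**The concern.** Families know their arm, and the outcomes are reports by the young person or the caregiver. For measures that a researcher collects in person, keeping that researcher unaware of allocation is a protection the trial could still have. An interviewer who knows the arm can, without meaning to, influence how a question is put, clarified or recorded.

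The protocol presents the loss of blinding as a fact and gives no reason for it, yet its own procedure hands the allocation to the role that will do the assessing. The measures at stake include the two pilot co-primary outcomes, caregiver-reported family functioning and self-reported conduct problems. The protocol keeps both so that intervention effects on them can still be tested. Family functioning and parental self-efficacy are also planned mediators, so the mechanism analyses would be affected as well.

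**Working it through.** No arithmetic applies. The check follows the allocation from the trials unit to the person who records outcomes.

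1. *Who generates it.* The trials unit does, after consent and baseline. No one who assesses needs to know the result at this point.
2. *Who passes it on.* The researcher tells the practitioner and the FFT-G supervisor. The documents give no reason why the trials unit could not tell them itself.
3. *Who collects outcomes.* A Greenwich researcher does, at every time point, from a team of at most four field staff (one Research Fellow plus up to three assistants). The protocol uses the same term for the person who relays and the person who assesses, and it does not separate the two tasks.
4. *What the protocol says about masking.* Blind at baseline, not blind at post-treatment. That sentence names the 6-month assessment only. If the role already holds the allocation, it still holds it at 12 months, the main time point, but this is an inference.
5. *Consistency.* The section aims for a research team that is blind to the randomisation outcome, and then has a member of that team report the outcome. The SAP repeats the aim without the relay. The two statements need reconciling.
6. *Which outcomes are exposed.*
   - ISRD4 primary outcome and exploitation items: self-completed, separate ID, stored elsewhere, with limited help from the researcher. Largely protected.
   - Caregiver-reported SDQ, SCORE-15, DASS-21 and BPSES: collected by the researcher and not described as using the anonymous route. Exposed if follow-up is by interview.
   - Young person's SDQ and SCORE-15: probably the same, but the protocol does not list every secondary outcome that uses the anonymous route.
7. *Safeguards.* Neither document provides a masked assessor, a request that families withhold their service, or a field recording whether the assessor was unmasked. Readers of the final report could not tell how far masking held.

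**The case against.** The strongest reply is that the plan is open about the unblinding and that much of it could not be prevented. Families know their arm, and some will mention it while answering questions about family life. The protocol gives no cause for the loss of blinding, and the sentence after it concerns families. The documents therefore do not establish that the relay is the reason. This stands: rerouting would close one route only. But disclosure by some families is no reason to give the allocation to the assessing role in every case.

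A second reply is that the aim of a blind team can be read as concealment of the next allocation, which varying block sizes serve. On that reading the passages sit awkwardly together rather than contradict each other. That is fair, and it is why the wording needs clarifying.

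Third, the documents name a role and not an individual. A reader might infer that the person who relays a family's allocation always interviews that family, or that every assessor is unmasked at every visit. The text does not say so; it only fails to prevent it.

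Fourth, interview mode is stated for baseline alone, with an online option. The exposure at follow-up rests on assuming the same mode.

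Finally, a reader might infer that the primary result is compromised. The handling of the ISRD4 data argues against that: the researcher does not see the full answers and another team holds the data. Help on request leaves a small opening at most.

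**Conclusion.** The concern holds as an avoidable design weakness and a wording conflict, disclosed but not justified. It bears mainly on researcher-collected secondary outcomes and mediators, and only slightly on the primary outcome. It rests on two assumptions: that follow-up is by interview as at baseline, and that the relaying and assessing roles are not kept apart in practice.

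The size of any bias cannot be derived from the documents. It is tempting to assume an interviewer effect in standard deviations and express it as a share of the planning effect of 0.36. The documents give no basis for such a figure, and 0.36 is the pilot effect for caregiver-reported family functioning, not for offending. Nor do they support a claim that knowing the arm would change how persistently families are traced. The point is best treated as a cheap improvement.

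**What to change.** - Have the trials unit notify the referring practitioner and the FFT-G supervisor directly, without going through anyone who recruits or assesses.
- Withhold allocation from outcome-collecting researchers in any shared tracker. The protocol mentions a joint tracker but does not say whether it shows allocation, so the rule should cover any such field.
- Ask families, before each follow-up assessment, not to say which service they received.
- Record at 6 and 12 months whether the assessor was unmasked, and report the counts by arm.
- In the protocol's Randomisation section, replace the statement that the researcher cannot be blind after baseline with one that the researcher is blind unless unmasked by the family. Reconcile this with the blind-team aim there and in the SAP, Design overview.

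The proposed Data and Referral Officer looks like an alternative relay, since the protocol says of that post: "They will have no role in the administration of research questionnaires or consent forms". But the post sits within the organisation delivering FFT-G, arranges first meetings with families, and may collect completed forms in sealed envelopes. Direct notification is cleaner.

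The cost is a change to the notification arrangement, access settings where a tracker shows allocation, a line in the assessment script and one data field. No new staff, sample size change or model change is needed. The downside is that some families will still unmask the assessor, so the gain is partial.

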A variant of FFT, FFT-Gangs, was found to be effective at engaging YP at high risk of gang involvement and was more effective in reducing recidivism at 18-month follow-up for high-risk youth (but not for low-risk youth) when compared to services as usual (SAU; Thornberry et al., 2018). We subsequently tested the feasibility of evaluating this intervention with YP at risk of CCE in UK child social care⁶. The results of this pilot RCT demonstrated that it was feasible to both implement FFT-G with this population and to evaluate it. The key results that informed the design of this efficacy study were:

1. Close alignment and shared recruitment systems between the project and evaluation team were key to successful recruitment of participants.
2. FFT-G therapists require a training period prior to randomisation starting in order to develop clinical skills and establish referral pathways. This should be a minimum of 6 months.

⁵ <https://www.blueprintsprograms.org/>

⁶ See <https://youthendowmentfund.org.uk/wp-content/uploads/2023/01/FFT-G.-YEF-Feasibility-and-Pilot.-Jan-2023.pdf>.

3. Information on risk factors is not captured and recorded reliably enough on agency systems in order to identify eligible YP (see p.65 of pilot study report). Further screening by the FFT-G supervisor/supervisor-in-training is required.
4. Between 10 and 11 eligible YP were identified per month. Randomisation rates were significantly higher when the FFT-G supervisor/supervisor-in-training screened agency systems for eligible cases rather than when they waited to receive referrals. Therefore, when screening of agency systems is conducted by the FFT-G supervisor/supervisor-in-training, we would expect 6 randomisations per site per month (see pp.56-59 of pilot study report).
5. Attrition was 20%. Missing data rates were very low but, as noted below, there were significant problems with some measures.
6. The upper end of the sample size projection (see sample size calculation section below) indicated a required sample size of 248, adjusted to 288 to account for 10% attrition at post-treatment and another 10% attrition at long-term follow-up (12 months post-randomisation). Therefore, an efficacy trial will most likely need to recruit across 3 sites over 16 months.

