Two co-primary outcomes were used: PCG reported family functioning (total scale score) and YP reported conduct problems (CP; subscore of the SDQ). Based on the effect size for PCG-reported Family Functioning outcome ($g = 0.36$ (-0.32,1.03)), clincalc.com returned 238 participants, increased to 288 to account for up to 10% loss to follow-up at each assessment time point. Based on the effect size for YP-reported CP ($g = 1.15$ (0.13,1.52)), clincalc.com returned 42 participants, increased to 51 to account for 10% loss to follow-up at each assessment time point. After discussion with the YEF Assistant Director of Evaluation, the decision was taken to use the upper end of this sample size calculation range (N=288). Any harmful effects will be monitored through serious incident reporting.

Table 2: Sample size calculation

		PARAMETER
Pilot study Effect Size		$g = 0.36$ [-0.32,1.03]
Pre-test/ post-test correlations	level 1 (participant)	0.523
Alpha ⁹		0.05
Power		0.8

⁹ Please adjust as necessary for trials with multiple primary outcomes, 3-arm trials, etc., when a Bonferroni correction is used to account for family-wise errors.

		PARAMETER
One-sided or two-sided?		One sided
Number of participants	Intervention	144
	Control	144
	Total	288

Outcome measures

Details on primary and secondary outcomes and other variables are provided below. Table 3 provides contextual information on the outcomes relating to offending and CCE.

Outcome data collection points

There are three data collection points: at baseline prior to randomisation; post-treatment: six months after randomisation; follow-up: twelve months after randomisation.

Unless specified below, all measures will be collected by a University of Greenwich researcher at all time points.

Table 3: Outcome terminology

Terminology	
Offending behaviours	Offending behaviours refer to behaviours that break the law. The YEF refer to three types of offending behaviours: (a) non-violent crime (viz. that do not involve violence against another person such as shoplifting, graffiti, using illegal drugs); (b) sexually violent crime; and (c) violent crime against another person (e.g., assault, robbery using threat or force, homicide)

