Therefore, the anticipated primary outcome in the pilot study was CCE as recorded on agency systems. During the pilot study, it became clear that this was not recorded reliably and so two co-primary outcomes collected directly from participants were used instead: PCG reported family functioning (total scale score) and YP reported conduct problems (CP; subscore of the SDQ). As a result, power calculations for this efficacy trial did not make use of SRD data from the pilot study. Based on the effect size for PCG-reported Family Functioning outcome in the pilot study (g = 0.36 (-0.32,1.03)), clincalc.com returned 238 participants, increased to 288 to account for up to 10% loss to follow-up at each assessment time point. Based on the effect size for YP-reported CP (g = 1.15 (0.13,1.52)), clincalc.com returned 42 participants, increased to 51 to account for 10% loss to follow-up at each assessment time point. After discussion with the YEF Assistant Director of Evaluation, the decision was taken to use the upper end of this sample size calculation range (N=288). Any harmful effects will be monitored through serious incident reporting. The pre-test/post-test correlation also mirrors the results of the pilot trial (i.e., 0.523).

However, as subsequently requested by the YEF, this trial will use self-reported delinquency as the primary outcome. The rationale for this is:

- A core YEF strategic aim is to understand what works to reduce crime and violence, so YEF aims to select offending as the primary outcome in all YEF studies where it is plausible that the intervention will reduce it, e.g. it is included in the theory of change
- The primary outcome must be measured using a valid and reliable measure and there were no valid and reliable measures of other relevant outcomes that are highly connected to crime e.g. child criminal exploitation.
- The mitigations included since the pilot study to increase the chance of seeing impact on offending (e.g. screening YP, introducing anonymous reporting of outcomes by YP)
- The co-primary outcomes from the pilot study will be included as secondary outcomes so that it will still be possible to test for intervention effects on these.

Participants

Participants will be YP between 10-17 at risk of CLDN involvement or CCE being seen by child social care or related agencies in three London local authorities and their primary caregiver (PCG).

Inclusion criteria - YP and families

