We use broader criteria identified by the Child Safeguarding Practice Review Panel (2020) for CCE/CLDN involvement, with a view to further screening undertaken subsequently in consultation:

Child/ young person aged between 10–17 years

AND

ONE OR MORE OF:

Known to services due to concerns in the last 12 months around:

Child sexual exploitation (CSE)

Child criminal exploitation (CCE)

Missing (from home or care) episodes

Potential or actual gang or CLDN affiliation as identified by police or other statutory service

Repeated school exclusion or absence

Involvement as a perpetrator or victim of youth violence or criminality

OR

TWO OR MORE OF THE FOLLOWING (OVER THE LAST 12 MONTHS):

Family conflict or inadequate supervision

Associating with antisocial peers

Concerns about alcohol or drug use

AND EITHER

Index child/young person is living at home 50% or more each week.

OR

Index child/young person is currently in an out of home placement, but with a clear return home plan (discussed on a case-by-case basis).

AND

Caregiver(s) and index child/young person are willing to engage in family therapy.

Exclusion criteria - YP and families:

- Index child/young person is actively homicidal, suicidal or psychotic.
- Problem sexual behaviour is the central concern.
- Presence of organic and/or cognitive conditions that may have prevented family members making use of talking therapy.
- Key family members, defined as "major players" in FFT-G, refuse family-based therapy.
- Significant child protection concerns: basic needs of children are not being met.
- Family have plans to move out of borough, thereby making therapy unfeasible within five months.

Analysis

We will test the effect of FFT-G on primary and secondary outcomes on an intention-to-treat basis using hierarchical linear mixed modelling, with post-treatment and baseline outcomes, trial arm and trial arm by time interaction term as explanatory variables (included in power calculations). Linear mixed models allow repeated measures from each participant to be correlated by fitting random intercepts varying at the level of the individual, thereby improving the precision of estimates. We will analyse differences in treatment outcomes in subgroups (e.g., by gender, age, temperamental irritability, CU traits and presence of offending behaviour at baseline identified by caseworker) by using interaction terms. We will

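### The stated one-sided inputs give 192 participants, not 238; the sample-size text needs reconciling and the sidedness of the primary test needs stating

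*Protocol*

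**What the plan says.** The Protocol (Sample size calculations, Table 2) and the SAP (Sample size calculations overview) give the same inputs.

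- **Effect:** g = 0.36, the pilot estimate for caregiver-reported family functioning, with interval -0.32 to 1.03.
- **Level and power:** alpha 0.05; "Estimates used 80% power"; allocation "with an enrolment ratio of 1".
- **Sidedness:** the table entry is One sided, and the text says "Power calculations used one-sided tests because there is no recorded case of FFT having iatrogenic effects".
- **Correlation:** the tables list 0.523, and the SAP adds "The pre-test/post-test correlation also mirrors the results of the pilot trial (i.e., 0.523").
- **Result:** "clincalc.com returned 238 participants, increased to 288 to account for up to 10% loss to follow-up at each assessment time point". A companion calculation for conduct problems, g = 1.15, is reported as 42, raised to 51.

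The Protocol's list of pilot results (Study rationale and background, item 6) gives a different starting figure: it "indicated a required sample size of 248, adjusted to 288".

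The Analysis section of each document describes a mixed model with baseline outcome and "trial arm by time interaction term as explanatory variables (included in power calculations"). The SAP's Presentation of outcomes section builds the Hedges' g interval from the 1 - alpha/2 normal quantile.

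**The concern.** A reader should be able to put the tabulated inputs into the standard formula and recover the stated N. Here a one-sided 5% calculation at g = 0.36 needs far fewer than 238, and using the correlation lowers the number further. At least one of the sidedness, the use of the correlation, or the description of 238 as the figure before attrition must therefore be wrong.

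Sidedness matters beyond the sample size because it can become the decision rule. The only sidedness the documents put in words is one-sided, while the only interval formula is two-sided. If the one-sided 5% label carried over to the analysis, a result with z between 1.645 and 1.960 would be called a benefit although its 95% interval included zero. The chance of a false claim of benefit would then be 5%, against 2.5% in that direction under a two-sided 5% test.

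**Working it through.** **Inputs.** g = 0.36, alpha = 0.05, power 80%, 1:1 and r = 0.523, all from the two sample-size sections and their tables. Normal quantiles: 1.645 (one-sided 5%), 1.960 (two-sided 5%), 0.842 (80% power).

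**1. Trying to reproduce 238.** Per arm, n = 2(z_alpha + z_beta)² / g². Baseline adjustment multiplies n by 1 - r² = 1 - 0.2735 = 0.7265 for ANCOVA, or by 2(1 - r) = 0.954 for a change score.

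| Calculation at g = 0.36 | One-sided 5% | Two-sided 5% |
|---|---|---|
| Unadjusted, per arm | 2(2.487)²/0.1296 = 95.4, so 96 | 2(2.802)²/0.1296 = 121.1, so 122 |
| Unadjusted, total | 192 (t-based 194) | 244 (t-based 246) |
| Change score, r = 0.523 | 184 | 232 |
| ANCOVA, r = 0.523 | 140 | 176 |

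No one-sided entry is near 238. At N = 238 the one-sided power for g = 0.36 is 87.1% unadjusted, or 94.7% with ANCOVA, not 80%.

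**2. Can rounding of g explain it?** For g from 0.355 to 0.365 the unadjusted total runs from 198 down to 186 one-sided, and from 250 down to 236 two-sided. The two-sided range contains both 238 and 248; the one-sided range contains neither. An exact 238 needs g of about 0.322 one-sided or about 0.363 two-sided.

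**3. Companion figure.** For g = 1.15 the same formula gives 20 (t-based 22) one-sided and 24 (t-based 26) two-sided. The stated 42 matches neither; it corresponds to g of about 0.77 one-sided or 0.86 two-sided.

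**4. Attrition.** 238 × 1.1 × 1.1 = 287.98, so 288. 42 × 1.21 = 50.8, so 51. The plan's inflation is thus reproduced as two multiplications by 1.1. To be left with the target after two 10% losses one divides: 238/0.81 = 293.8, so 294, and 42/0.81 = 51.9, so 52. Starting from 248 gives 300 (× 1.21) or 306 (÷ 0.81), so 248 does not lead to 288 by either route.

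**5. What 288 provides.** 288 × 0.81 = 233.3 expected completers at 12 months. Two-sided power = Φ(g√(N/4) - 1.960):

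- Unadjusted: 0.36 × √(233.3/4) = 2.749; Φ(0.789) = 78.5%.
- ANCOVA with r = 0.523: 2.749/√0.7265 = 3.226; Φ(1.266) = 89.7%.
- With a flat 20% loss (230 analysed): 78.0% and 89.4%.

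**The case against.** The strongest reply is that the calculator's actual inputs are not in the documents, so nobody outside the team can say what produced 238. That stands. Two-sided unadjusted at the printed g gives 244, not 238, and other routes come close. A two-sided change score using r = 0.523 gives 232 at g = 0.36, and 238 at g = 0.355 (124.56 × 0.954 = 118.8, so 119 per arm). One route is exact at the printed g: one-sided 96 per arm divided by 0.81 is 118.5, so 119 per arm and 238 in total. That would make the one-sided label right, but attrition would then have been counted twice to reach 288, and both documents present 238 as the calculator's output before any allowance for loss. The unexplained 42 shows further that the printed effect sizes do not fix the inputs. A reader might infer that 238 simply is the two-sided, unadjusted number and that r was never used. The documents do not support that as fact.

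A second reply is that the one-sided label belongs to the power calculation alone. That also stands. Neither document says the primary test is one-sided, and the SAP interval points the other way, so a reader who infers that the trial will test at one-sided 5% goes beyond the text. Nor is harm ignored: both documents say harmful effects will be tracked through serious incident reports.

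A third reply is that N does not change. True, but the text from which N is derived is still wrong under every route above.

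**Conclusion.** The stated inputs do not reproduce the stated sample size. As labelled they give 192 (140 with ANCOVA), against 238, and rounding of g cannot account for the difference. A two-sided 5% calculation is the likelier source but is unproven. The inflation to 288 falls 6 short of the 294 that two successive 10% losses require, leaving about 233 completers. That shortfall is small: two-sided unadjusted power is 79.3% at 238 and 78.5% at 233. The figures 238 and 248 contradict each other, and 42 is not reproduced.

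The sidedness of the primary test is unstated. The inflated false-positive rate and the claim of benefit with an interval spanning zero follow only if the one-sided label is carried into the analysis.

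It would be tempting to add that the one-sided choice gains nothing because 288 already pays for a two-sided test. The figures do not go that far. Unadjusted two-sided power is just under 80%, and it reaches 89.7% only if r = 0.523 applies. The effect size is from pilot family functioning, r is described only as a pilot result, and both documents say pilot delinquency data were not used. None of these figures therefore establishes power for ISRD4.

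**What to change.** 1. State in the Protocol and SAP that the primary test is two-sided at 5%, in line with the SAP's interval. Change the One sided entry in both tables, and amend the sentence justifying one-sided tests to agree.
2. Rerun the calculation and report its actual inputs, including an unrounded g. Say whether r = 0.523 was used and, if so, how. If it was not, correct the remark in both Analysis sections that the model terms were part of the power calculation.
3. Reconcile 238 with 248, and check 42. Only the authors know which inputs were entered, so these should be corrected from their records.
4. Keep N = 288. Replace the attrition statement with about 233 expected completers at 12 months, and give two-sided power of 78.5% unadjusted, or 89.7% if r = 0.523 applies. Say that both are for the pilot family-functioning effect and not for ISRD4.

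The cost is wording and table edits, with no extra participants. The downside is that stated unadjusted power falls slightly below 80%. The sidedness of the test should be fixed before the separately held primary-outcome data are linked to the main study IDs. The SAP update listed in the Protocol timeline is one opportunity.
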